Acute stroke system	Centralising	Centralised 2010	Centralising	Centralising
Rurality	Rural	Urban	Rural	Rural

Note. ¹East Kent eligibility was initially for patients where there was diagnostic uncertainty, and changed to all suspected strokes in September 2020.

Workstream 1: implementation and experiences [RQs 1&2; months 1-24]

The study will use a range of qualitative methods to analyse implementation and sustainability of prehospital triage services for stroke, and stakeholder experiences of these services, including patient, carer, and healthcare professional perspectives. The approach will draw on the chosen conceptual framework for implementation and sustainability of digital innovation,^[28] and it will be informed by the developing findings from the team's recent service evaluation of the NC London and East Kent services.

Stakeholder interviews

In each of the four case sites, up to 30 interviews will be conducted with a wide range of stakeholders to ensure suitable coverage of the services studied and the context in which they operate. Interviewees will include stroke and non-stroke (initially suspected to be stroke) patients and their carers, including patients with different decisions resulting from assessment (i.e., transferred to stroke unit, transferred to emergency department, referred to TIA clinic, advised to stay home). The team will work closely with clinical colleagues (including local research nurses) and purposively sample interviewees to ensure that a diverse range of patients and carers is recruited, in order to reflect local socio-demographic factors, including ethnicity, socio-economic status, language capabilities (e.g. non-English speakers) and living situation (e.g. patients who live alone). Interviews will also be conducted with clinical and managerial staff in ambulance services, acute stroke teams, and emergency departments, senior organisational management, and representatives of the wider context (Table 2).

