Note. ^AControl for stroke patients is national, whereas the control for Ambulance data combines four NHS Ambulance trusts –meaning the stroke patient control is proportionally larger than the ambulance data control. ^BStroke case numbers drawn from the Stroke Sentinel National Audit Programme (SSNAP) data for April 2019 to March 2020. ^CNational data cover England, Wales, and Northern Ireland, excluding strokes reported for the case sites. ^DEast Kent data combine strokes reported for two sites: Queen Elizabeth the Queen Mother Hospital and William Harvey Hospital. ^EMaidstone data combine strokes reported for two sites: Maidstone General Hospital and Tunbridge Wells Hospital, the latter of which closed in late 2019, with stroke activity transferred to Maidstone. ^FAmbulance call sample based on estimates of 12 months of calls where ambulance crews have categorised patients as 'suspected stroke/neurological event', as provided by LAS, SECAmb, WMAS, and NEAS.

To study prehospital care, analyses will focus on job cycle time (from 999 call to 'ambulance free' time, where the ambulance is ready for its next dispatch); and initial patient destination. As these patient-level data are not held nationally the team will request these data from local ambulance services identified above. The team have confirmed with these organisations that the data are collected reliably and are available for request; and the costs agreed for these data requests have been included in the budget. Over the course of data requests researchers will work closely with Ambulance service representatives to ensure consistency of definitions and data collection. To study delivery of acute stroke care and stroke patient functional independence, researchers will analyse patient-level stroke national clinical audit data requested from SSNAP, and data collected by stroke teams using prehospital video triage. To study patient outcomes (patient mortality and length of hospital stay), researchers will analyse Hospital Episode Statistics data linked with Office for National Statistics mortality data, requested at patient-level from NHS Digital.

Source	Data	Measures	Time
Local ambulance	Patient-level	Call categorisation, Emergency Operations Centre	Apr 2019-

Table 4.Quantitative data sources

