	Patients categorised by ambulance crews as suspected stroke/neurologica	 Job cycle length, disaggregated by Time to dispatch; to scene; on scene; to hospital; Total job cycle Patient destination 	Aug 2022
Local stroke units	Patient-level	Stroke services using prehospital triage are collecting data on destination and diagnosis of all patients categorised as non-stroke	Apr 2019- Aug 2022
SSNAP	Patient-level Data for patients categorised as stroke	 Type of stroke (infarction/haemorrhage) Stroke severity (NIHSS¹) on arrival Patient characteristics (e.g. sex, age) Arrival mode (e.g. by ambulance, inhospital) Eligibility for thrombolysis Eligibility for mechanical thrombectomy Time from a) symptom onset, b) 999 call, and c) arrival at hospital to brain scan admission to stroke unit thrombolysis (if eligible) mechanical thrombectomy (if eligible) assessment by consultant physician assessment assessment by stroke specialist nurse swallow screen Outcomes: Functional independence: patients with Modified Rankin Scale score (established measure of stroke patient disability) of 0-2 (or return to baseline if baseline score is more than 2)	Apr 2019- Aug 2022
HES/ONS	Patient-level ED attendances (with dates); Stroke attendances	Emergency hospital admissions with dates and length of hospital stay All-cause patient mortality at 30 and 90 days	Apr 2019- Aug 2022

Note. ¹NIHSS=National Institutes of Health Stroke Scale.

Workstream 3: cost-effectiveness [RQ4; months 1-24]

In addition to understanding the effectiveness of pre-hospital triage it is also important to evaluate the cost-effectiveness of the intervention. Where possible the analyses will seek to understand if different triage systems deliver variable outcomes and costs, thereby informing any wider national scale-up.

The health economic analysis will focus on the case study sites and national and regional controls (Table 3). The analyses will draw on the same data sources as requested for Workstream 2 (Table 4), along with national reference costs and Trust estimates of service costs.

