Workstream 2. Patient conveyance, care delivery, and patient outcomes

The hypothesis is that prehospital video triage will a) reduce the number of inappropriate patient transfers to specialist stroke units, which will b) result in hyperacute treatments being delivered to stroke patients more quickly and reliably than elsewhere, and therefore c) that stroke patients treated by such services will have better outcomes than those treated by services that do not use prehospital video triage. To test these hypotheses, the analysis will use a controlled before-and-after design to estimate the impact of prehospital triage on ambulance journeys for suspected stroke patients:

Patient destination: the hypothesis is that there will be a significant reduction in the proportion of patients classified as 'suspected stroke/neurological' who are transferred to hospitals with specialist stroke units following implementation of prehospital triage services, relative to control sites.

The study will also analyse 'Job cycle' length (i.e., time from initial 999 call received through to 'ambulance free'), disaggregated by key processes (Table 4)

Furthermore, the analysis will estimate the impact on stroke patients receiving key clinical interventions, including:

- Time from onset of symptoms to receiving clinical interventions (to assess potential impact of increased time on scene to conduct prehospital triage)
- Time from arrival at hospital to receiving clinical interventions (to assess potential benefits of prehospital triage and advance knowledge of patients on effective running of stroke teams)
- Impact of these services on the following key outcomes
 - Patient mortality at 90 days (the primary outcome)
 - Patient functional outcome (as measured with the Modified Rankin Scale)

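### 90-day mortality and mRS are analysed in stroke patients identified from hospital records, a group whose membership triage may change, and the plan has no check for a differential shift

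*Protocol*

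**What the plan says.** Section 9, Workstream 2, lists 90-day mortality (primary) and mRS beneath the statement that "the analysis will estimate the impact on stroke patients receiving key clinical interventions". Its outcome hypothesis is that "stroke patients treated by such services will have better outcomes than those treated by services that do not use prehospital video triage". The outcome population is therefore stroke patients.

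Section 4, Workstream 2, names the sources. For mortality and length of stay, "researchers will analyse Hospital Episode Statistics data linked with Office for National Statistics mortality data". The HES/ONS row of Table 4 describes the records as "ED attendances (with dates); Stroke attendances". For mRS the source is SSNAP, whose row begins "Patient-level Data for patients categorised as" stroke. Only job cycle and destination are taken from the ambulance cohort of suspected stroke, and no section links that cohort to HES/ONS or SSNAP.

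Triage has four possible outcomes, set out where Section 4 describes the interviewees: "transferred to stroke unit, transferred to emergency department, referred to TIA clinic, advised to stay home". Section 1 asks whether more patients remain at home and avoid admission. Section 9 matches on patient variables that triage should not alter, with sex and age as examples.

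**The concern.** The patients in whom the outcomes are measured are identified at hospital, after triage has acted, and triage is intended to influence who gets there. A true stroke that is kept at home, referred to a TIA clinic or never coded as stroke can drop out of the group that carries the primary outcome. If such losses change in case areas after implementation by more or less than they change in controls, the DiD compares groups of different composition. The mortality difference then mixes any effect of triage with a change in case mix.

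Section 9 protects the matching covariates by excluding variables that triage could alter. Membership of the cohort gets no such protection, and matching on variables such as age and sex cannot restore a shift in severity. NIHSS appears only under SSNAP and is recorded on arrival, so it exists only for those who arrive.

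The consequence reaches beyond the primary result. In Workstream 3 a DiD supplies the effect size and the linked HES/ONS data supply the mortality estimates, so a case-mix artefact would pass into the cost per QALY.

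**Working it through.** The protocol gives no baseline mortality, effect size, alpha or power figure, so there is no stated number to reproduce. The check is case-mix arithmetic on assumed inputs.

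**Inputs**

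- From Table 3: case-site strokes per year 970 + 1,457 + 789 + 515 = 3,731; control 85,549 per year.
- From Table 1 and the data window (April 2019 to August 2022, which counts to 41 calendar months): months after implementation are 29 (East Kent), 28 (NC London), 23 (Maidstone) and 22 (Darent Valley), counting the start month as after.
- Assumed, not in the protocol: 90-day mortality p = 15% in all strokes; a share d of strokes lost from the recorded group because of triage; mortality m in those lost.

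**Step 1. Shift in recorded mortality when nobody's outcome changes**

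Recorded mortality = (p − d·m)/(1 − d).

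| d | m | Strokes lost per year | Recorded mortality | Shift (points) |
|---|---|---|---|---|
| 3% | 2% | 112 | 0.1494/0.97 = 15.40% | +0.40 |
| 5% | 2% | 187 | 0.1490/0.95 = 15.68% | +0.68 |
| 10% | 2% | 373 | 0.1480/0.90 = 16.44% | +1.44 |
| 3% | 5% | 112 | 0.1485/0.97 = 15.31% | +0.31 |
| 10% | 0% | 373 | 0.1500/0.90 = 16.67% | +1.67 |
| 5% | 15% | 187 | 15.00% | 0 |
| 5% | 25% | 187 | 0.1375/0.95 = 14.47% | −0.53 |

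The last two rows show that the sign depends on who is lost. For d = 10% and m = 2%, putting the lost patients back gives 0.9 × 16.44% + 0.1 × 2% = 15.0%, so the shift is pure composition.

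**Step 2. A yardstick for size**

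- Case sites after: 970×29/12 + 1,457×28/12 + 789×23/12 + 515×22/12 ≈ 8,200.
- Case sites before: 970×12/12 + 1,457×13/12 + 789×18/12 + 515×19/12 ≈ 4,547.
- Control, split roughly 27 months after and 14 before: 85,549×27/12 ≈ 192,485 and 85,549×14/12 ≈ 99,807.
- Binomial SE without clustering: √[0.15×0.85×(1/8,200 + 1/4,547 + 1/192,485 + 1/99,807)] ≈ 0.675 points.
- Detectable effect at 80% power, two-sided 5%: (1.96 + 0.84) × 0.675 ≈ 1.9 points.

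The shifts at m = 2% are therefore about 21%, 36% and 76% of the detectable effect for losses of 3%, 5% and 10%.

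**Step 3. Chance of a nominally significant false difference (p = 15%)**

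With d = 10% it is about 61% (m = 1%) or 48% (m = 3%). With d = 2% it is about 7% for either m, close to nominal. Clustering would widen the SE and change these figures.

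**The case against.** Several stronger readings are tempting, and the protocol does not support them.

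- **That mortality is measured only in patients recorded as stroke.** This is literal for mRS. For mortality it is inferred from Section 9, because the HES/ONS row also lists ED attendances. Those are still people who reached hospital, and no mortality analysis of all suspected strokes is described.
- **That losses occur only in case areas after implementation.** Nothing says that non-conveyance, TIA referral or death at home is absent beforehand or in controls. Only a differential change biases a DiD.
- **That everyone redirected is lost.** Triage aims mainly to divert non-strokes, which leaves a stroke denominator unchanged, and a stroke sent to an ED and coded there stays in HES. Exposure is also partial: Darent Valley assesses only uncertain cases, 50 of 168 hours a week, and East Kent covered only uncertain cases until September 2020.
- **That triage will make mortality look worse.** That holds only if those lost are milder than average.

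It can also be said that every input to the size is assumed, that sex and age are examples and not a full list, that robustness tests are promised, and that a selection check could sit in an analysis plan not seen here. All of this is fair and limits the size and severity of the point. It does not remove it: the protocol itself fixes the outcome population and sources, and none of the safeguards it describes addresses a change in who enters that population.

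**Conclusion.** The point holds as a should-fix. The mortality and mRS cohorts are formed from hospital records after an intervention intended to change who is conveyed, the upstream ambulance cohort has no outcome linkage, and the matching described does not correct a change in severity.

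The direction and size of any bias are unknown. Under an assumed 15% mortality and 2% mortality in those lost, losses of 3% to 10% would add 0.4 to 1.4 points with no true effect, against roughly 1.9 points detectable without clustering. At losses near 2% the distortion is negligible, and it reverses if those lost are sicker than average. A reader might infer that the primary result will be biased towards harm, or that it is uninterpretable; the documents support neither. They support only that, without a check, neither an apparent benefit nor an apparent harm can be attributed to triage with confidence.

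**What to change.** In Section 9, Workstream 2, add the following.

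1. The same DiD applied to the monthly number of recorded strokes, NIHSS on arrival and the share of mild strokes (with the NIHSS cut-off stated), reported beside the primary result. The SSNAP data for this are already requested.
2. A statement that the mortality and mRS estimates are read as triage effects only if no differential shift is seen. This is best judged on the confidence interval, because the count check has limited precision: with Poisson counts and no overdispersion, its SE on the log scale is √(1/8,200 + 1/4,547 + 1/192,485 + 1/99,807) ≈ 0.019. That gives a 95% interval of about ±3.7% and 80% power for a shift of about 5.3%. A 3% loss could pass unseen, though at m = 2% it moves mortality by only 0.4 points.
3. If a shift is seen, a bounding analysis that adds back the shortfall in recorded strokes over a stated range of assumed mortality. The range has to be assumed, because NIHSS is in SSNAP, mortality is in HES/ONS, and no link between them is stated.

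Section 4 should also say whether the mortality cohort includes ED attenders not coded as stroke.

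Optional: a DiD on counts of 90-day stroke deaths with a population offset, which hardly moves when mild survivors leave the denominator. It needs area population figures that are not in Table 4 and does not capture deaths among people who never reach hospital.

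The cost of items 1 to 3 is analysis wording, with no new patients or data. The downside is a more conditional headline for the primary outcome.

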2 BACKGROUND AND RATIONALE

Stroke is a major cause of death and disability.^[1] Stroke patients have better care and outcomes if treated in a specialist unit.^[2-5] Not every hospital has a specialist stroke unit: patients are commonly triaged by prehospital clinicians, bypassing the nearest emergency department if a patient is thought to be suffering a stroke. Many patients present with stroke-like symptoms but have another condition which 'mimics' a stroke. This may be difficult to determine in the prehospital setting with the assessment deemed 'false positive',^[6] and the patient making an unnecessary journey to a specialist stroke team when in fact an alternative health care setting may be more appropriate (comprising up to 50% of all presentations to specialist stroke teams). This places avoidable pressure on ambulance and stroke services, with serious implications for quality of care for stroke and non-stroke patients.^[7] Remote prehospital triage may increase appropriate patient transfer, improving effectiveness and efficiency of ambulance, stroke, and other services, and the quality of care and outcomes for stroke and non-stroke patients.

During the first wave of the COVID19 pandemic, ambulance, and stroke teams in North Central (NC) London and East Kent developed and implemented prehospital video triage services, which used digital tools technology to permit remote communication between ambulance clinicians and stroke specialists. Through these services, stroke specialists can assess the patient while the patient is still on scene of the 999 call. The aim was to optimise individual patients' care: to ensure that stroke patients were taken to a stroke unit, and to minimise the number of non-stroke patients making unnecessary journeys to a stroke unit or hospital emergency departments (ED) if they could be managed by their GP or as an outpatient; these issues are important at any time, but became particularly urgent during the pandemic.

Reviewing existing evidence

Through a current service evaluation (discussed below),^[8] the team are conducting a two-phase literature review to assess the existing evidence base. The initial phase was a 'review of reviews' to identify existing systematic, scoping and narrative reviews on prehospital triage for

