This research will take place in four areas of London and South East England where prehospital triage for stroke has been established. The focus of the research is on prehospital ambulance care and acute care settings, including stroke and emergency departments, but will also explore the organisations within which these services sit, and the wider context, including local/regional governance and commissioning, the voluntary sector, and other patient representative groups. In preparing the research application the team engaged with ambulance service leads in England and Wales, and clinical leads in Scotland (through the National Ambulance Stroke Leads group), who confirmed no other areas have implemented services of this kind at equivalent scale. Through this engagement with wider networks, the team were made aware of activity on prehospital triage for stroke in the East of England (plans to introduce a service, beginning with a pilot), and London (aims to roll out NC London model across the city). The team have engaged with people leading this activity in each area to ensure they are aware of this research, and they will to be added to the prospective stakeholder list (discussed further under Dissemination).

The study will analyse four case sites where prehospital triage has been implemented, summarised in Table 1. While similar in terms of platform and function, these case sites vary on a number of key features of the conceptual framework, including intervention characteristics (e.g., 24/7 coverage or patient eligibility), organisational characteristics (e.g. NHS Foundation trust status and academic links), and wider context (e.g., stroke system, rurality).

Characteristics	Case site				
	East Kent	NC London	Maidstone	Darent Valley	
Intervention characteristics					
Implemented from	Apr-2020	May-2020	Oct-2020	Nov-2020	
Platform	Facetime	Facetime	Facetime	Facetime	
Eligibility for assessment	All suspected strokes ¹	All suspected strokes	All suspected strokes	Diagnostic uncertainty	
Assessor	Consultant/ registrar	Consultant/ registrar	Stroke nurse, then consultant if needed	Stroke nurse, then consultant if needed	
Hours active	24/7	24/7	Stroke nurse: 24/7 Consultant: 8am- 8pm Mon-Fri	8am-6pm Mon- Fri	

Table 1. Characteristics of case sites

Organisation characteristics				
Acute FT-status	Yes	Yes	No	No
Acute Teaching	Yes	Yes	No	No
ED & Stroke unit co- located	No	No	Yes	Yes
Ambulance service	SECAmb	LAS	SECAmb	SECAmb
Wider context				

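### Times to consultant and stroke-nurse assessment are not limited to assessment after arrival, so if video calls are entered in the audit the difference-in-differences counts the intervention as its own effect

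*Protocol*

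**What the plan says.** Protocol Section 4 gives SSNAP the role of measuring in-hospital care: "To study delivery of acute stroke care and stroke patient functional independence, researchers will analyse patient-level stroke national clinical audit data requested from SSNAP". The SSNAP row of Table 4 sets three clock starts, beginning "Time from a) symptom onset, b) 999 call, and c) arrival at hospital to brain scan". The end points that follow are stroke unit admission, thrombolysis, thrombectomy, assessment by a consultant physician, "assessment by stroke specialist nurse" and swallow screen.

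Section 9, Workstream 2, gives the clocks different meanings. Onset-based times are to show whether longer time on scene does harm. The arrival-based measure, "Time from arrival at hospital to receiving clinical interventions", is to show whether advance knowledge of patients helps stroke teams run well. Effects are estimated by difference-in-differences (DiD) against areas without triage.

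Section 2 describes the intervention: "stroke specialists can assess the patient while the patient is still on scene of the 999 call". Table 1 gives the assessor as "Consultant/ registrar" at East Kent and NC London, and "Stroke nurse, then consultant if needed" at Maidstone and Darent Valley.

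**The concern.** For two of the listed process times, the event that stops the clock is of the same kind as the intervention: a specialist assessing the patient. Before start, and in control areas throughout, that event takes place after arrival. At case sites after start it may already have taken place by video. The Protocol does not say whether a video call counts as the consultant or nurse assessment, and does not limit either item to in-person assessment.

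If calls are entered as the assessment, the DiD shows an improvement on the arrival clock even if nothing changes in hospital, and Section 9 invites the reading that stroke teams are running better. The onset clock shortens too. That is the clock Section 9 relies on to detect harm from longer time on scene, so a real delay could be masked on these two items. Subtracting the control change does not help, because controls have no video calls.

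**Working it through.** The plan states no figure on this point, so there is none to reproduce. The check has two parts.

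**1. What each recording rule does to the arrival-based item**

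| Cell | Call entered as the assessment | Call not entered |
|---|---|---|
| Control, before and after | post-arrival time | post-arrival time |
| Case sites, before | post-arrival time | post-arrival time |
| Case sites, after, triaged | zero or negative | post-arrival time |

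Only the middle column changes the definition between cells. Under the right-hand column the item is the same quantity in all four cells.

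**2. How much of the treated-after cell could be exposed**

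Inputs:
- Annual strokes (Table 3): East Kent 970, NC London 1,457, Maidstone 789, Darent Valley 515; total 3,731.
- Hours (Table 1): East Kent and NC London 24/7. Maidstone nurse 24/7, consultant 8am-8pm Monday to Friday = 12 × 5 = 60 hours. Darent Valley 8am-6pm Monday to Friday = 10 × 5 = 50 hours. A week has 168 hours, so 60/168 = 36% and 50/168 = 30%.
- Assumptions: arrivals spread evenly over the week; every stroke in service hours is triaged; every East Kent and NC London call is made by a consultant; every nurse call within consultant hours is passed on to the consultant.

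Consultant item: (970 + 1,457 + 789 × 60/168 + 515 × 50/168) / 3,731 = (2,427 + 281.8 + 153.3) / 3,731 = 2,862.1 / 3,731 = 76.7%.

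Nurse item: (789 + 515 × 50/168) / 3,731 = (789 + 153.3) / 3,731 = 942.3 / 3,731 = 25.3%.

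These use annual counts as weights. Weighting by months in service to August 2022 instead (29, 28, 23 and 22) gives a total of 970 × 29 + 1,457 × 28 + 789 × 23 + 515 × 22 = 98,403. The consultant item becomes (28,130 + 40,796 + 18,147 × 60/168 + 11,330 × 50/168) / 98,403 = 80%, and the nurse item (18,147 + 11,330 × 50/168) / 98,403 = 22%. The picture is the same.

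**Size of the artefact.** If a share s of treated-after strokes is recorded at zero, and those patients would otherwise have had the same mean time m as the rest, the mean becomes (1 − s)m. It falls by the fraction s, and by more if negative times are kept. The range is therefore 0 (no calls entered) to about 77% for the consultant item and 0 to about 25% for the nurse item.

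In minutes, the artefact in the DiD is s × shift. The documents give no times, so take an assumed shift of 30 to 60 minutes: up to 0.767 × 30 = 23 to 0.767 × 60 = 46 minutes on the consultant item, and 0.253 × 30 = 8 to 0.253 × 60 = 15 minutes on the nurse item.

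**The case against.** Four counter-arguments deserve weight.

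- **The artefact depends on an entry rule that the documents do not give.** This stands, and it makes the point conditional. A reader might infer that the items are compromised whichever rule applies, since a triaged patient seen in hospital is being seen for the second time. The documents do not support that. If calls are not entered, the item is post-arrival assessment in every cell, and being seen sooner or later after triage is a consequence of the intervention that the DiD is meant to capture. Section 9 names that very mechanism.
- **Section 9 does not name these items.** It speaks of clinical interventions without listing consultant or nurse assessment, and Table 4 is a table of data sources. This stands in part: that these times will be used to claim benefit is an inference. But Table 4 is the only place where the times are listed, and Section 4 uses SSNAP to study care delivery.
- **The plan already promises to understand the data.** Section 9 commits the team to work with clinical partners and data owners in months 1-5, and field definitions may be in a SAP that is not shown. This lowers the importance. It does not name the issue, and the stated care to avoid variables altered by triage covers the matching variables only.
- **Exposure does not divide neatly by site.** A reader might infer from Table 1 that the consultant item is exposed at two sites (2,427 of 3,731, 65%) and the nurse item at the other two (35%). That is not supported. Consultants can join calls at Maidstone and Darent Valley; a registrar's call may not count as a consultant assessment; and Darent Valley runs for 50 of 168 hours and takes only cases of diagnostic uncertainty.

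**Conclusion.** A conditional point on two secondary process measures holds. As written, nothing in the Protocol prevents a pre-arrival video assessment from stopping the clock for consultant or nurse assessment. If sites entered calls that way, the DiD on these items would partly measure the intervention itself; if they did not, there is no artefact.

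The 77% and 25% are upper bounds. Registrar calls, nurse calls not passed to a consultant, strokes not arriving by ambulance, the Darent Valley eligibility limit and the narrower East Kent eligibility before September 2020 all lower them. Arrivals concentrated in weekday hours would raise the Maidstone and Darent Valley parts.

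The primary outcome, 90-day mortality, is untouched, and times to brain scan, stroke unit admission, thrombolysis, thrombectomy and swallow screen need the patient to be in hospital. Importance is low to moderate.

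**What to change.** - In Table 4 and Section 9, Workstream 2, define both items as the first in-person assessment after hospital arrival, in all four DiD cells.
- When specifying the data request, ask the four case sites how video calls were entered in the audit, and whether this changed over time.
- Check for assessment times before arrival, and treat them as evidence of exposure to video triage, not as outcome values.
- If video and in-person assessments cannot be separated, report the two items descriptively and rest the arrival-based benefit claim on brain scan, stroke unit admission, thrombolysis, thrombectomy and swallow screen.

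The cost is one definition, one query to four sites and one data check. The downside is that two secondary process measures may become descriptive.
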